1. STUDY OBJECTIVES

The primary objective of this trial is to evaluate the effectiveness, safety, and acceptability of combining cytisine with nicotine e-cigarettes plus text-based behavioural support (TBS), compared to cytisine plus TBS or nicotine e-cigarettes plus TBS, on six-month smoking abstinence.

We hypothesise that cytisine plus nicotine e-cigarettes and TBS is more effective at helping smokers quit than cytisine plus TBS. Furthermore, cytisine plus nicotine e-cigarettes and TBS is more effective at helping smokers quit than nicotine e-cigarettes plus TBS.

2. STUDY DESIGN

Please refer to the study protocol for a full description of the trial design. This is a single-blind, pragmatic three-arm, parallel group, randomised trial. Participants will be recruited nationwide, using multi-media advertising with targeted promotion to reach Māori, Pacific and low socio-economic groups given their disproportionately higher smoking prevalence.

Potential participants interested in the trial will register on a trial website. Participants will be asked for on-line consent to complete an online screening questionnaire to determine their eligibility for the trial and verify their phone number. Eligible and interested participants will then provide online consent to enter the trial.

A copy of the consent form and participant information sheet will be automatically emailed by the online system to the participant for their records. Participants will also be asked to provide online consent to inform their general practitioner that they are participating in the trial. Via the online platform the baseline data will be collected, and then participants will immediately be randomised to either 12 weeks of: 1) cytisine plus nicotine e-cigarette, 2) cytisine; or 3) nicotine e-cigarette.

All 12-weeks of trial products will be couriered to participants immediately after randomisation. The courier company will notify the study centre immediately after the courier pack has been delivered, which will trigger the scheduling of the 'quit date' follow-up call and the start of the text-based behavioural support programme. Participants will be asked to begin their treatment the day after they receive their courier pack and to reduce their smoking *ad libitum* over the first four days of treatment so that they are not smoking at all by the fifth day ('quit date').

Participants will be called on their quit date to verify they are quitting on that day (and to collect outcome data). If a participant states that they are not quitting on the scheduled 'quit date', they will be given one chance to reset their quit date within the next seven days, with this date becoming their new 'quit date' (which will trigger the scheduling of all subsequent follow-up calls). For participants who are unable to be contacted at quit date, their 'quit date' will be set in the system as six days after they received their courier pack (which will trigger the scheduling of all subsequent follow-up calls). Participants will be advised to continue with their allocated treatment irrespective of any lapses back to smoking.

Outcome assessments will be undertaken at one, three, and six months after the Quit date, and at 12 months in a subsample. At the six-month follow-up, in-person carbon monoxide tests will be performed for participants who live in the Auckland region to verify self-reported continuous smoking abstinence.

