4. STUDY OUTCOMES

4.1. Primary outcome

Verified six-month continuous abstinence (using Russell Standard) defined as self-report of smoking not more than five cigarettes from the Quit date and confirmed by an expired air carbon-monoxide (CO) measurement with a Bedfont Smokerlyzer (≤ 9 ppm signifying abstinence). Biochemical validation of self-reported cessation for Auckland participants will involve a researcher visiting participants within 72 hours if they claim to be abstinent, to obtain a CO reading. For participants outside of Auckland who self-report that they are smokefree, verbal consent will be sought from them to provide their contact details to their region's community-based smoking cessation service, so that they can undertake the CO monitoring within 72 hours. Sensitivity analysis will be undertaken looking at different cut-offs for the CO measurement, given lack of consensus about the best reading to use

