7.5. Primary outcome analysis

The proportion of participants that have been biochemically verified as continuously abstinent at six months by group will be analysed using log-binomial regression, and the risk in each group, relative risks, absolute risk differences, and corresponding 95% confidence intervals will be calculated. All analyses for the

primary outcome will be ITT (unless otherwise stated) and include all randomised participants. Missing outcomes will be imputed using multiple imputation assuming the data is missing at random. Multiple imputed datasets will be created (n=50) and the imputation model will include baseline age, sex, and group, and the fully conditional specification logistic regression method will be used to impute the missing outcomes. The imputed datasets will be analysed using log-binomial regression and combined to output one inference. Adjusted analyses for potential covariates will be conducted if needed.

To check the robustness of the primary outcome the following sensitivity analyses will be conducted:

- self-reported continuous abstinence at 6 months (not biochemically verified)
- using the following varying cut-offs used for CO measurements: ≤ 3 ppm, ≤ 5 ppm, ≤ 8 ppm

The following sensitivity analyses will also be conducted for the primary outcome where groups will be compared using chi-squared tests:

- complete case analysis
- per protocol analyses where participants that have any major protocol violations will be excluded (see 6.2)
- assuming all missing outcomes are still smoking instead of using multiple imputation

Tests for heterogeneity will be used to examine if there is any difference in the groups on the unadjusted primary outcome for the following subgroups: baseline age (will be dichotomised based on the median), sex, ethnicity (Māori, non-Māori), education (< 12 years of attending school, 12 or more years of attending school), type of cigarettes smoked (RYO, factory made, both), AUDIT-C (low, high), cannabis use, motivation to quit, level of cigarette dependence (using HSI), and level of behavioural support received (will be categorised based on the data). Subgroup analyses will also be conducted by batch number of product received (Batch 1: early 2022, Batch 2: early 2023) to assess if there were any differences by batch.

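### Self-reported abstainers with no CO reading would, on the natural reading of SAP 7.5, be imputed from age, sex and arm alone, which lowers verified quit rates and the risk difference; section 2 should also be aligned with 4.1 on where tests are done

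*SAP*

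**What the plan says.** Section 2 states that "Participants will be recruited nationwide". For six-month verification it says that "in-person carbon monoxide tests will be performed for participants who live in the Auckland region", and it mentions no other region.

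Section 4.1 defines the primary outcome as self-reported continuous abstinence from the quit date, confirmed by CO of at most 9 ppm. It gives two routes to the reading:

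- **Auckland:** "Biochemical validation of self-reported cessation for Auckland participants will involve a researcher visiting participants within 72 hours".
- **Elsewhere:** "For participants outside of Auckland who self-report that they are smokefree, verbal consent will be sought from them" to pass their details to the region's cessation service, "so that they can undertake the CO monitoring within 72 hours".

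Section 7.5 analyses "The proportion of participants that have been biochemically verified as continuously abstinent at six months by group" in all randomised participants. It continues: "Missing outcomes will be imputed using multiple imputation assuming the data is missing at random", and "the imputation model will include baseline age, sex, and group". Neither six-month self-report nor region is in that model.

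The listed sensitivity analyses include self-report without verification, other CO cut-offs, complete cases, and missing counted as smoking. Nowhere does the SAP say how to classify a participant who reports abstinence but has no CO reading.

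**The concern.** There are two linked problems.

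**Wording.** Sections 2 and 4.1 describe different coverage of the test on which the primary outcome depends.

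**Imputation.** This problem remains when 4.1 is followed to the letter. Outside Auckland a reading depends on a further consent and on a third party acting within 72 hours, so some readings will be missing. A participant who reports smoking is a failure without any test. Absent readings therefore arise only among self-reported abstainers. Whether the outcome is missing then depends on six-month self-report, which the trial collects but the imputation model leaves out, so the data are not missing at random given age, sex and arm. A person who says they have quit is assigned the success rate of an arm made up mostly of smokers.

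At stake are the verified abstinence rate in each arm, the risk difference between arms, and the power to detect it.

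**Working it through.** **1. The plan's own figure.** Section 2.4 states 90% power with 300, 300 and 200 participants, rates of 25%, 12% and 9%, and 28% loss. After loss, 300 × 0.72 = 216 and 200 × 0.72 = 144 remain. With a two-sided test at 0.025 per comparison (my assumption for the stated allowance for multiple testing), power is 89.5% for 25% v 12% and 96.0% for 25% v 9%. The stated figure reproduces and is not in dispute.

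**2. Inputs for the bias.**

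| Input | Value | Source |
|---|---|---|
| True verified rate p | 25% (combination), 12% (cytisine), 9% (e-cigarette) | SAP 2.4 |
| CO pass share v among self-reported abstainers | 85% | assumed |
| Auckland share, all tested | 33% | assumed |
| Uptake of testing elsewhere | 50% | assumed |

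The share of self-reported abstainers tested is f = 0.33 + 0.67 × 0.5 = 0.665. Untested abstainers are assumed to pass CO at the same rate as tested ones.

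**3. Formula.** Self-reported abstinence is s = p / v. Observed successes are s·f·v. Observed outcomes are all self-reported smokers plus tested abstainers, 1 − s(1 − f). Imputing the rest at the observed arm rate gives an expected estimate of s·f·v / [1 − s(1 − f)]. Loss that is random within arm cancels from this ratio.

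**4. Results.**

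- Combination: s = 0.25/0.85 = 0.294; 0.16625 / (1 − 0.294 × 0.335) = 0.16625 / 0.9015 = 18.4%.
- Cytisine: s = 0.12/0.85 = 0.141; 0.0798 / (1 − 0.141 × 0.335) = 0.0798 / 0.9527 = 8.4%.
- E-cigarette: s = 0.09/0.85 = 0.106; 0.05985 / (1 − 0.106 × 0.335) = 0.05985 / 0.9645 = 6.2%.

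| Comparison | True difference | Expected estimate | True RR | Expected RR |
|---|---|---|---|---|
| Combination v cytisine | 13 points | 10.1 points | 25/12 = 2.08 | 2.20 |
| Combination v e-cigarette | 16 points | 12.2 points | 25/9 = 2.78 | 2.97 |

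In the combination arm an untested abstainer is thus given an 18.4% chance of success, against the 85% seen in tested abstainers.

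**5. Range over the untested share.** This is a separate calculation for 25% v 12%, with v = 0.80 (assumed). Power comes from 1,000 simulated trials with 50 imputations by arm, 28% random loss and a two-sided 5% test of the risk difference. The last column is 13 × (1 − untested share).

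| Untested share of self-reported abstainers | Imputed rates | Difference (points) | Power | Difference if untested = smoking (points) |
|---|---|---|---|---|
| 0% | 25.0% v 12.0% | 13.0 | 93.9% | 13.0 |
| 20% | 21.3% v 9.9% | 11.4 | 89.4% | 10.4 |
| 35% | 18.2% v 8.2% | 10.0 | 84.5% | 8.45 |
| 50% | 14.8% v 6.5% | 8.3 | 75.9% | 6.5 |
| 65% | 11.0% v 4.7% | 6.3 | 63.1% | 4.55 |

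**6. Do the listed sensitivity analyses repair this?** No. Complete-case analysis has the same expected value as step 3. Counting missing as smoking lowers the difference further. The self-report analysis drops verification. None of them estimates verified abstinence using the self-report that is known.

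**7. Does using self-report repair it?** Among self-reported abstainers the tested pass rate is 85%. Applying it to the untested gives s·v = 0.294 × 0.85 = 25% and 0.141 × 0.85 = 12%, so the 13 points are recovered under the assumption in step 2.

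**The case against.** **Section 2 may simply be brief.** It refers the reader to the protocol for the full design and does not say that testing is confined to Auckland. Section 4.1, which defines the outcome, agrees with it on Auckland and adds the other route. This stands. A reader might infer that nobody outside Auckland is tested. On the inputs of step 2 with f = 0.33, that would give 10.3% v 4.4%, a difference of 5.9 points, but it requires section 4.1 to be ignored. Section 2 is an incomplete summary, not a rival rule.

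**The SAP does not say that untested abstainers are imputed.** This also stands. Because 4.1 requires confirmation, not verified could be read as not abstinent. Treating an absent reading as a missing outcome is the more natural reading of 7.5, but it is a reading. The alternative also shrinks the difference, to 13 × 0.665 = 8.6 points on the inputs of step 2, so the lack of a rule is itself part of the problem.

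**Not every effect measure moves towards no effect.** Correct. Section 7.5 also reports relative risks, and these rise slightly, from 2.08 to 2.20 for the first comparison.

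**Most missing outcomes are not untested abstainers.** Correct. A reader might infer that they are, but 28% loss is planned. On the inputs of step 2, untested abstainers are 0.72 × 0.294 × 0.335 = 7.1% of the combination arm and 0.72 × 0.141 × 0.335 = 3.4% of the cytisine arm. Even if no one were tested they would be 0.72 × 0.294 = 21% and 0.72 × 0.141 = 10%, still below 28%. Random loss does not alter the bias.

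**Missing tests do not remove successes alone.** Correct. Some untested abstainers would have failed the CO test, and the 85% pass share allows for that.

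**Conclusion.** The point holds in two parts. Section 2 is incomplete beside 4.1 and should be aligned with it. More importantly, 7.5 neither classifies a self-reported abstainer without a CO reading nor, on its natural reading, imputes that person suitably. The result is a downward bias in verified rates and in the risk difference: about 10 points instead of 13 when roughly two thirds of self-reported abstainers are tested. The relative risk moves slightly away from 1.

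The size rests on assumed values for the Auckland share, the uptake elsewhere and the CO pass rate, none of which the SAP gives, and on untested abstainers passing at the same rate as tested ones. If the untested would pass less often, the bias is smaller. The direction holds for the combination arm as long as their pass rate exceeds the imputed arm rate (18.4% in the example).

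The documents do not support reading the plan as restricted to Auckland, or treating the 5.9-point figure as its expected result.

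**What to change.** **Section 2:** reword the sentence to match 4.1, so that a CO reading is sought from every self-reported six-month abstainer, by researcher visit in Auckland and through the community service elsewhere.

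**Section 7.5, classification:** state that a self-reported smoker at six months is a failure, and that a self-reported abstainer with no CO reading has a missing verification.

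**Section 7.5, imputation in two steps:**

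1. For those lost to follow-up, impute six-month self-reported abstinence from age, sex, arm and earlier self-report.
2. Among self-reported abstainers only, observed or imputed, impute the CO result from age, sex and arm, adding region (Auckland or elsewhere) if readings exist outside Auckland.

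Simply adding self-report to the single logistic model would not work. Every self-reported smoker is a failure, so the model would suffer separation, and self-report is itself missing for those lost. A region effect cannot be estimated if no one elsewhere is tested.

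Keep missing counted as smoking as a sensitivity analysis, and report by arm and region how many self-reported abstainers were tested.

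**Cost:** SAP wording and somewhat more programming. Self-report is already collected, and region should be known from the courier delivery. No procedure is needed beyond 4.1.

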2.1. Eligibility criteria

Participants will be eligible for inclusion if they:

- Are daily smokers who live in New Zealand
- Are at least 18 years of age
- Want to quit smoking in the next 2 weeks
- Are able to provide online consent
- Have access to a mobile telephone that can text and have access to the internet via a computer or smart phone
- Are willing to use cytisine or an e-cigarette or both products to help quit smoking

Exclusion criteria:

- Are pregnant or breastfeeding or if they are women trying to become pregnant in the next three months
- Currently using smoking cessation medication (including daily use of an e-cigarette for the last month)
- Are enrolled in another smoking cessation program or trial
- Have known hypersensitivity to cytisine, or nicotine e-cigarettes
- Have a strong preference to use or not to use cytisine and/or e-cigarettes in their quit attempt
- Self-report that they have moderate or severe renal impairment, are undergoing treatment for active or latent tuberculosis, have experienced a myocardial infarction, stroke, or severe angina within the previous two weeks, have uncontrolled high blood pressure (>150 mmHg systolic, >100 mmHg diastolic) or have a history of seizures
- Have another person in their household involved in the trial

2.2. Study intervention

Participants allocated cytisine will be instructed to follow the manufacturer's 25-day dosing regimen:

- days 1-3: one tablet (1.5mg) every two hours through the waking day (six tablets/day)
- days 4-12: one tablet every 2.5 hours (five tablets/day)
- days 13-16: one tablet every three hours (four tablets/day)
- days 17-20: one tablet every 4-5 hours (three tablets/day)
- days 21-25: one tablet every six hours (two tablets/day)

However, a maintenance dose of cytisine will be added for day 26 to week 12 (one tablet every six hours: two tablets/day).

Participants allocated a nicotine e-cigarette will be instructed to follow the manufacturer's instructions for use, with ad libitum use over 12 weeks. The e-cigarette device used in the trial will be the 'UpOX', a closed pod system with a 3% nicotine salt (30mg/mL). A tobacco flavour e-liquid will be provided as this is the usual flavour chosen by smokers when they are transitioning away from tobacco. Participants will be advised that they should try and use only the product provided,

but if they are finding the nicotine strength is not sufficiently addressing their cravings (or the flavour is distasteful) they are free to try alternative nicotine strengths or flavours, but that this will be at their own cost). Participants will be asked at follow-up about any switching of products. The content of the nicotine e-liquid supplied will be independently assessed (by LabTech Scientific and Technical Services, Auckland) to verify nicotine content is as labelled. Batch-to-batch variability in nicotine content in the e-liquids will also be assessed.

All participants will receive the text-based behavioural support STOMP programme (developed and tested by the National Institute of Health Innovation, University of Auckland). This text message programme provides personalised smoking cessation advice, support, and motivation to support individuals to quit smoking and maintain cessation. The programme includes messages covering information relevant to quitting, tips to cope with cravings, advice on avoiding smoking triggers, and motivational support. The programme includes 2-way functionality to support individuals during cravings and is personally tailored. Regular, personalised text messages providing smoking cessation advice, support, and distraction will be delivered over a six-month period (five messages a day for six weeks, then three per week until the end of the 26th week – i.e., six-month follow-up).

2.3. Randomisation

All participants who fulfil eligibility criteria will be randomly allocated in a 3:3:2 ratio to one of the 3 treatment groups using block randomisation, and stratified by ethnicity (Māori, non-Māori). The randomisation sequence will be prepared by the study statistician and loaded into a secure database.

2.4. Sample size

A sample size of 800 (N=300 in the cytosine group, N=300 in the cytosine plus nicotine e-cigarette group, and N=200 in the nicotine e-cigarette group) will provide 90% power at two-sided $p=0.05$ to detect an absolute difference of 13% in six-month smoking abstinence rates between the combination treatment group and the cytosine group, and 16% difference between the combination treatment group and the nicotine e-cigarette group (taking account of multiple testing).

The predicted difference is based on trial evidence for six month verified continuous abstinence quit rates of 9% for nicotine e-cigarettes, 12% for cytosine, and 25% for combination cessation treatment (averaged). The sample size accounts for a 28% loss-to-follow-up at six months.

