7. STATISTICAL ANALYSIS

All statistical analyses will be performed using SAS version 9.4 and R version 3.4.2. Data collected in the NIHI Redcap database will be extracted into SAS for the analyses. All statistical tests will be two-tailed and a 5% significance level throughout the analyses. No adjustments for multiplicity are planned for any of the outcomes.

Summaries of continuous variables which are normally distributed will be presented as means and standard deviations or medians and inter-quartiles for skewed data, while categorical variables will be presented as frequencies and percentages. Continuous variables will be compared with t-tests or Mann-Whitney tests and categorical data with chi-squared tests as appropriate.

A separate EXCEL file containing the SAP tables specific to this study will be provided based on all the analyses stated below (see Appendix I).

All regression analyses will be conducted for the following two comparisons:

- Cytisine plus nicotine e-cigarette group vs Cytisine only group
- Cytisine plus nicotine e-cigarette group vs Nicotine e-cigarette only group

Exploratory analyses will also be conducted comparing the Cytisine only and Nicotine e-cigarette only groups for the primary outcome.

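### SAP 2.4 claims 90% power with multiple testing allowed for, but section 7 plans no adjustment; at the 5% level planned, the two powers are about 94% and 98%

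*SAP*

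**What the plan says.** Section 2.4 plans 800 participants: 300 on cytisine, 300 on the combination and 200 on the nicotine e-cigarette. This agrees with the 3:3:2 allocation in section 2.3. The sample "will provide 90% power at two-sided $p=0.05$ to detect an absolute difference of 13% in six-month smoking abstinence rates" against cytisine, and the same sentence adds a "16% difference between the combination treatment group and the nicotine e-cigarette group", with a note in brackets that multiple testing has been allowed for. The expected abstinence figures are "quit rates of 9% for nicotine e-cigarettes, 12% for cytosine, and 25% for combination cessation treatment (averaged"), and 28% loss to follow-up at six months is said to be included. The method of adjustment and the adjusted significance level are not given.

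Section 7 sets a two-tailed 5% level for all analyses and adds: "No adjustments for multiplicity are planned for any of the outcomes". It names two comparisons for all regression analyses, combination against cytisine and combination against e-cigarette. A third, cytisine against e-cigarette, is exploratory.

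**The concern.** There are two linked problems.

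The first is a contradiction about the significance level. Section 2.4 sizes the trial with an allowance for testing two hypotheses, and section 7 then tests both without one. For either primary comparison, a p-value between 0.025 and 0.05 would count as success under section 7. It would not under the adjusted level that section 2.4 appears to have used. Section 7.6 also makes the cost analyses depend on a significant primary outcome, so the level decides more than a label.

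The second is that one power figure cannot be the power of both comparisons. They have different control rates (12% and 9%), different control-arm sizes (300 and 200) and different assumed effects (13 and 16 points). At any one significance level they have different powers, and 90% can match at most one of them.

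**Working it through.** **Inputs, all from section 2.4 unless noted**
- Randomised: combination 300, cytisine 300, e-cigarette 200.
- Loss 28%, so evaluable: 300 × 0.72 = 216, 216, and 200 × 0.72 = 144.
- Abstinence: combination 25%, cytisine 12%, e-cigarette 9%.
- Significance level: two-sided 0.05 (section 7), or 0.05/2 = 0.025 if the unnamed adjustment is Bonferroni for two comparisons (assumption).

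**Formula** (two-proportion z-test, pooled variance under the null)

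Power = Φ[(d − z·s0)/s1], where
- d = p1 − p2
- s0 = √[p̄(1 − p̄)(1/n1 + 1/n2)], with p̄ the pooled rate
- s1 = √[p1(1 − p1)/n1 + p2(1 − p2)/n2]
- z = 1.960 at 0.05 and 2.241 at 0.025.

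The unpooled version replaces s0 by s1.

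**Step 1. The plan's own figure: 25% against 12%, 216 against 216**

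p̄ = 0.185, s0 = 0.03736, s1 = 0.03684, d = 0.13.
- At 0.025: (0.13 − 2.241 × 0.03736)/0.03684 = 1.256, power 89.5% (unpooled 90.1%). This reproduces 90%.
- At 0.05: (0.13 − 1.960 × 0.03736)/0.03684 = 1.541, power 93.8% (unpooled 94.2%).

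The match at 0.025 supports both the assumed adjustment and the way the loss was applied.

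**Step 2. The second comparison: 25% against 9%, 216 against 144**

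p̄ = (216 × 0.25 + 144 × 0.09)/360 = 0.186, s0 = 0.04186, s1 = 0.03791, d = 0.16.
- At 0.025: (0.16 − 2.241 × 0.04186)/0.03791 = 1.746, power 96.0%.
- At 0.05: (0.16 − 1.960 × 0.04186)/0.03791 = 2.057, power 98.0%.

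**Step 3. Does the choice of method explain the gap?** Power for 25% against 9%:

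| Method | 0.025 | 0.05 |
|---|---|---|
| Pooled | 96.0% | 98.0% |
| Unpooled | 97.6% | 98.8% |
| Arcsine | 96.6% | 98.3% |
| Continuity-corrected | 94.4% | 97.2% |
| Fisher exact | 95.8% | 97.9% |
| Missing counted as smoking (rates × 0.72, 300 against 200) | 94.7% | 97.3% |

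An adjustment for three comparisons (0.05/3) gives 94.3% pooled and 92.3% with continuity correction, but at that level the cytisine comparison falls to 86.5% (pooled). None of these variants brings the e-cigarette comparison within 2 points of 90%.

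**Step 4. Summary**

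| Level per comparison | 25% vs 12% | 25% vs 9% |
|---|---|---|
| Stated in 2.4 | 90% | 90% |
| 0.025 (assumed Bonferroni) | about 90% | about 96% |
| 0.05 (section 7) | about 94% | about 98% |

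**The case against.** The best defence is that a single power for two comparisons is often the figure for the limiting one. Read that way, 90% belongs to the comparison with cytisine, where it reproduces, and the e-cigarette comparison simply exceeds it. This is a fair account of how the figure probably arose. However, section 2.4 does not call 90% a minimum or tie it to one comparison, and the reading works only at a level that section 7 does not use.

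The figure might also be meant as the probability that both comparisons succeed. By simulation that is about 88% at 0.025 each and 93% at 0.05 each. These values lie on either side of 90%, and neither matches it.

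The 0.025 is inferred. The SAP names no method, and the 96% depends on that inference. The 94% and 98% at the planned 5% level do not.

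Three stronger conclusions might be drawn, and the SAP does not support them:
- **That 16 points is offered as the smallest detectable difference.** Section 2.4 presents the differences as predictions from the assumed rates (25 − 12 = 13 and 25 − 9 = 16), not as a detection limit.
- **That a null result would be misread.** Section 7.5 reports relative risks, risk differences and 95% confidence intervals. These, not the planning power, govern how a null result is read.
- **That the sample size is wrong.** At the assumed rates and loss, power is about 90% or more for both comparisons at either level by the standard pooled or unpooled formula.

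**Conclusion.** The point holds as a minor one, with two parts. Sections 2.4 and 7 contradict each other on whether the two primary comparisons are adjusted for multiplicity. The single 90% is also not the power of both: at 0.025 each it fits the cytisine comparison (89.5% to 90.1%), while the e-cigarette comparison has about 96% (94% to 98% by formula). At the 5% level actually planned, the powers are about 94% and 98%, and 90% fits neither.

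The misstatement is conservative, since the trial has more power than it claims, and enrolment is not affected. The contradiction over the level matters more than the surplus power. These results rest on the SAP's own rates and loss, on evaluable numbers of 216, 216 and 144, and, for the 0.025 figures, on an assumed Bonferroni split over two comparisons.

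**What to change.** Choose one significance level for the two primary comparisons, state it in both section 2.4 and section 7, and give each comparison its own power in 2.4:
- **If adjusted:** two-sided 0.025 each, about 90% for 25% against 12% and about 96% for 25% against 9%. Name the method in 2.4, and amend section 7 so that its statement on multiplicity excepts these two comparisons.
- **If unadjusted:** two-sided 0.05 each, about 94% and about 98%. Delete the reference to multiple testing from 2.4 and leave section 7 as it stands.

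The choice should be made before the outcome data are analysed. Either option changes SAP wording only and needs no change to enrolment. The adjusted option still leaves about 90% power or more for each comparison.
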